10.6 Occurrence of Hepatocellular Carcinoma in Patients with NAFLD

Any liver tumor occurrence will, in all cases, be diagnosed at the site according to local standard of care practices. In the event of a suspected tumor, subjects should undergo any confirmatory investigations that may be required.

These confirmatory investigations should be performed as soon as possible and in all cases within 21 days of diagnosis. All confirmatory investigations, including any additional scans that may be required, will be the responsibility of the study site.

If, after performing any confirmatory investigations that may be required, the diagnosis of malignancy is confirmed, the subject should immediately and permanently cease administration of study drug. Subjects with confirmed malignancy may then receive any other therapies or treatment modalities that their attending physicians consider appropriate.

However, such subjects should be encouraged to remain in the study and complete all scheduled visits, evaluations and assessments as per the protocol. If the subject elects not to participate in remaining visits, they should be strongly encouraged to complete a 'premature withdrawal' visit or early discontinuation visit as detailed in Section 10.4.

10.7 Death

In the event of a death on study, the investigator should complete the 'death' page of the Case report form (CRF), including the date and reason of death. All attempts should be made to secure access to any autopsy findings and to retrieve the patient compliance diary. The cause of death must be immediately notified to the CRO as a serious adverse event as described in Section 12.1 and, if applicable, to institutional review boards and / or local regulatory authorities, even if the death is considered to be due liver-related mortality.

10.8 Withdrawal of Consent

If a subject voluntarily elects to discontinue participation in the study, administration of study drug must be immediately and permanently ceased. However, such subjects should be encouraged to continue completing all scheduled visits, evaluations and assessments as per the protocol. If a subject elects not to participate in remaining visits, they should be strongly encouraged to complete a 'premature withdrawal' visit, encompassing:

- Recording of adverse events
- Review of concomitant medications and therapies
- Physical examination and vital signs

Completion of end of treatment visit at time of withdrawal

11.0 STUDY ASSESSMENTS

11.1 Clinical Efficacy Endpoints

The clinical endpoints of this study is time to remission (TTR). TTR is defined as time in weeks from randomization to improvement in hepatic steatosis as measured b MRI and liver function remission as defined as two consecutive ALT values within normal range (< 20 U/mL for woman and < 30 U/L for men) or 20% reduction from the baseline during study period.

11.2 Safety Assessments

11. 2.1 Clinical Safety Assessments

Physical examination and vital signs will be assessed monthly. Subjects must sit quietly for 5 minutes before having their pulse and blood pressure recorded.

All adverse events will be collected from the onset of study drug treatment. Serious adverse events are to be reported immediately to the CRO. Pre-dosing signs and symptoms will be recorded in the screening section of the CRF.

11.2.2 Laboratory Safety Assessments

All laboratory tests following randomization will be performed by a study approved laboratory service. Samples will be drawn at sites and forwarded under appropriate conditions to the approved laboratory. The laboratory will communicate all test results to site study personnel. The Laboratory Assessing Physician will immediately notify sites of any values which lie outside pre-specified ranges. Screening samples, prior to initiation of study drug, may be analyzed at site.

Sites will be immediately notified of any test results that lie outside of pre-specified ranges. Site personnel will not be expected to transcribe results from the laboratory into the CRF, although abnormal results that are considered clinically significant should be entered in the CRF as adverse events. Screening assessments, prior to initiation of study drug, may be performed at sites. Sites are discouraged from performing additional routine investigations locally, but site personnel are permitted to perform any investigations at any time that may be necessary to safeguard patient welfare.

11.3 Pharmacokinetics and Exposure/Response Assessments

Pharmacokinetics of JKB-121 will be assessed by measuring the plasma concentrations of JKB-121 at the steady state (Day 1) in three subjects in each treatment dose, i.e. 5 mg and 10 mg twice daily with the agreement of the patients. The exposure/response relationship of JKB-121 will be explored by measuring the plasma concentrations of JKB-121 in the sparse samples collected in all subjects and correlating them with the changes from baseline in ALT.

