1.1 TABLE OF EVENTS

	Screening Period	Enrollment	Treatment period							End of Treatment	Follow-up Visit
			2	3	4	5	6	7	8		
Visit	0	1	2	3	4	5	6	7	8	9	
Week	up to 4 wks	0	2	4	8	12	16	20	24	28	
Day (Visit Window)	-1 to -28	1	14 (± 4)	28 (± 4)	56 (± 4)	84 (± 4)	112 (± 4)	140 (± 4)	168 (± 4)	196 (± 4)	
Determination of eligibility	X	X									
Review of medical history	X	X									
Obtain informed consent	X										
Randomization		X									
Study drug dispensing		X	X	X	X	X	X				
Managing drug accountability			X	X	X	X	X	X	X	X	
Vital signs	X	X	X	X	X	X	X	X	X	X	
Physical exam	X	X		X	X	X	X	X	X	X	
Serum hCG (if applicable)	X										
Urine hCG (if applicable)		X		X	X	X	X	X	X	X	
Hematology panel	X	X	X	X	X	X	X	X	X	X	
Comprehensive metabolic panel	X	X	X	X	X	X	X	X	X	X	
Lipid panel		X		X	X	X	X	X	X	X	
Glycosylated hemoglobin	X	X		X	X	X	X	X	X	X	
HOMA-IR	X	X		X	X	X	X	X	X	X	
Urinalysis	X					X				X	
Electrocardiogram	X					X				X	
Liver biopsy (if prior biopsy > 12 mo)	X										
PK study		X*			X		X		X		
Review concomitant meds	X	X	X	X	X	X	X	X	X	X	
Review adverse events **		X**	X	X	X	X**	X	X	X**	X	
MRI for hepatic steatosis	X					X				X	
CK-18		X				X				X	
Stored serum for exploratory measures and noninvasive biomarkers of fibrosis		X				X				X	
Exit Interview											X

* Frequent sampling PK study on Day 1 for Substudy subjects only. All patients to have a pre-dose trough level drug measures (6 ml blood) at treatment Weeks 8, 16, and 24 (Visits 4, 6, and 8).

** Hospital Anxiety and Depression Scale and Columbia Suicide Severity Scale

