10.3.3 Enrollment Visit (Day 1, Visit 1)

Subjects returning to the clinic for randomization at Day 1 must be in a fasted state for at least 8 hours prior to sample collection prior dosing for this visit, which is a requirement for some of the blood test that will be performed as noted below.

Subjects will be randomized to study drug kit assignment and receive their Subject Identification Number prior to the first dose of study drug being administered. The following will be performed for all subjects who meet the inclusion criteria and not of the exclusion criteria

- Confirm that the subject continues to be eligible for participation
- Record vital signs
- Record weight
- Physical examination
- Hospital Anxiety and Depression Scal and Columbia Suicide Severity Scale Questionnaires.
- Complete blood samples for:
 1. Complete blood count with differential
 2. Blood chemistry including: ALT, AST, albumin, alkaline phosphatase, bicarbonate, BUN, calcium, chloride, creatinine, glucose, LDH, magnesium, phosphorus, potassium, sodium, total and direct bilirubin, protein, uric acid, and GGT.
 3. Fasting glucose and insulin level for HOMA-IR
 4. Lipid panel
 5. Glycosylated hemoglobin
 6. Urine pregnancy test (only for women of childbearing potential).

7. Serum and plasma samples for non-invasive biomarkers related to liver injury pathophysiology and/or TLR-4 pathway
8. ELF™ test—Subjects must be an a fasted state prior to the sample collection
9. FibroSURE/ FibroMAX/ FibroTest—Subject must be in a fasted state prior to the sample collection
10. Additional blood sample needs to be collected for pharmacokinetic study.
 - Counsel subjects on weight loss, diet and exercise
 - Record any adverse events occurring after signing of the informed consent form
 - Record all medications that the subject has taken since prior visit
 - Dispense study drug

10.3.3.1 PK Substudy Subjects Only: From volunteered subjects for intensive pharmacokinetic studies: Blood samples will be obtained *prior to 12 hour dosing* (predose and at 0.25, 0.5, 0.75, 1.0, 1.5, 2.0, 3.0, 4.0, 6.0, 8.0, 10, 12, and 24 (next day) hours post dose administration in three volunteered subjects from each treatment group (5 mg and 10 mg bid). Additional pre-dose blood sample for trough PK level at Day 1, weeks 8, 16, and 24 will be collected for assessment of steady state PK analysis as well as biomarker study.

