## 6.10 Pharmacokinetic Analysis

### 6.10.1 Sample Collections for Pharmacokinetic Analysis

Six mL of blood will be collected from fasting (at least 8 hours) subjects on Day 1 prior to dosing, and during Visits 4, 6, and 8 for measurements of the plasma concentrations of

JKB-121. In a subset of volunteers who consent to participate in PK Substudy, blood samples will be collected on Day 1 pre-dose and at each sampling point post-dose for PK evaluation.

From volunteered subjects for intensive PK studies: Blood samples will be obtained on Day 1 prior to 12 hour dosing (predose and at 0.25, 0.5, 0.75, 1.0, 1.5, 2.0, 3.0, 4.0, 6.0, 8.0, 10, 12, and 24 (next day) hours post dose administration in three volunteered subjects from each treatment group (5 mg and 10 mg bid). Additional pre-dose blood sample for trough PK level at Day 1, weeks 8, 16, and 24 will be collected for assessment of steady state PK analysis as well as biomarker study.

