### 6.10.2 Pharmacokinetic Variables

The following noncompartmental PK parameters will be calculated from plasma samples prior to the 12 hour dosing collected for the PK Substudy Population if data allows:

- Area under concentration-time (AUC) curve from time 0 to infinity (AUCinf)
- AUC curve from time 0 to time of last quantifiable concentration (AUClast)
- AUC curve from time 0 to 12 hours (AUC12h)
- Minimum post-dose concentration (Cmin)
- Maximum post-dose concentration (Cmax)
- Time of Cmax (Tmax)
- Apparent first-order terminal elimination rate constant calculated by linear regression of the terminal linear portion of the log concentration vs. time curve (Kel)
- Terminal phase elimination half-life (t1/2)
- Clearance (CL/F)
- Volume of Distribution (Vz/F)
- Percent AUC Extrapolated (AUC%extrap)

Parameters Kel, t1/2, and AUCinf will not be presented for those subjects who do not exhibit a terminal elimination phase in their concentration versus time profiles. In order to estimate the constant Kel, linear regression of concentration in logarithm scale vs. time will be performed using at least 3 data points. Uniform weighting will be selected to perform the regression analysis to estimate Kel. The constant Kel will not be assigned if the terminal elimination phase is not linear (as appears in a semi-logarithmic scale), the terminal elimination rate constant indicates a positive slope (Kel < 0), if the Tmax is one of the 3 last data points, or the regression coefficient (R^2) is less than 0.8.

The actual time relative to dosing will be used in the PK parameter calculation. The Linear Up/Log Down method will be used in the computation of all AUC values. The AUClast will

be calculated from 0 hour to the last time point with quantifiable concentration. The AUCinf will be calculated as AUClast + Clast/Kel, where Clast is the last quantifiable plasma concentration.

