If one or more non-quantifiable (NQ) values occur in a profile before the first measurable concentration, they will be assigned a value of zero. If a single NQ value occurs between measurable concentrations in a profile, the NQ should generally be omitted (set to missing). NQs which occur after the last measurable concentration will be omitted (set to missing).

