### **6.10.3 Pharmacokinetic Summary and Analysis**

PK concentration data will be summarized for each time point using descriptive statistics from the Safety Population and PK Substudy Population (i.e., Mean, SD, Minimum, Maximum, Median, %CV, Geometric Mean, Geometric %CV) by treatment group. Plots of mean concentrations of plasma concentrations (with standard deviation bars) versus nominal time will be generated for each treatment. Individual plasma concentration versus actual time plots will also be provided.

The PK parameters will be summarized by treatment group using the PK Substudy Population. Geometric mean and geometric coefficient of variation (CV%) will be added to the descriptive statistics for Cmin, Cmax, and all AUCs.

Trough (pre-dose) concentrations at Week 8, Week 16, and Week 24 will be summarized by treatment group for the Safety Population. If any trough concentration is NQ, it will be set to zero prior to summarization. Plots of mean trough concentrations (with standard deviation bars) by visit will be generated for each treatment.

The relationship between PK and efficacy may be explored as needed.

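### The Day 1 PK profile follows the first dose but is called steady state, and the SAP's Cmin rule can return an absorption-phase sample or a zero instead of an end-of-interval value

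*Protocol*

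**What the plan says.** **Timing.** Protocol 11.3 plans "measuring the plasma concentrations of JKB-121 at the steady state (Day 1) in three subjects in each treatment dose". The Table of Events (Protocol 1.1) puts the "Frequent sampling PK study on Day 1 for Substudy subjects only". Protocol 10.3.3 makes Day 1 the visit at which subjects are randomized, "prior to the first dose of study drug being administered". SAP 6.10.1 agrees on the day: "Blood samples will be obtained on Day 1 prior to 12 hour dosing", with samples "predose and at 0.25, 0.5, 0.75, 1.0, 1.5, 2.0, 3.0, 4.0, 6.0, 8.0, 10, 12, and 24 (next day) hours post dose", in three volunteers from each active dose group. SAP 6.10.1 and Protocol 10.3.3.1 also name the Day 1 pre-dose sample, together with the Week 8, 16 and 24 troughs, as samples for steady-state assessment.

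**Definition of Cmin.** SAP 6.10.2 computes the noncompartmental parameters from samples taken before the 12-hour dose and lists Cmin as "Minimum post-dose concentration". The protocol synopsis calls it the minimum observed concentration. Neither restricts it to times after Tmax or to the end of the dosing interval.

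**Zeros.** SAP 6.10.2 says that if non-quantifiable "values occur in a profile before the first measurable concentration, they will be assigned a value of zero". SAP 6.10.3 adds: "Geometric mean and geometric coefficient of variation (CV%) will be added to the descriptive statistics for" Cmin, Cmax and all AUCs.

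**The concern.** A profile taken after the first dose in subjects who are just starting treatment cannot be at steady state, so Protocol 11.3 contradicts the schedule. A pre-dose sample drawn before any drug cannot inform steady state either.

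The Cmin rule is a separate problem. A minimum over the whole post-dose window works at steady state, where the profile starts and ends near the trough. After a first oral dose the profile starts at zero, so the minimum may be whichever sample was drawn earliest. Cmin could then mean different things in different subjects: a 0.25 h value in one and a 12 h value in another.

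The PK profile in NASH is the first-listed secondary objective, and the synopsis names Cmin, Cmax and AUC as endpoints. At stake is whether the reported Cmin can be read as a trough, and whether first-dose parameters are presented under the right label.

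**Working it through.** The documents give no power or precision figure for PK, so there is nothing to reproduce. They also give no half-life, absorption rate, lag or assay limit; Protocol 3.5 says only that the compound is long-acting. All kinetic values below are therefore assumptions.

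**Inputs from the documents.** First dose on Day 1 (Protocol 10.3.3); twelve post-dose samples from 0.25 h to 12 h (SAP 6.10.1); twice-daily dosing, so a nominal 12 h interval; three subjects per active dose.

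**Model.** One compartment, first-order absorption, no lag: C(t) ∝ exp(−ke·t) − exp(−ka·t), with ke = ln 2 / half-life. This curve rises and then falls, so the lowest post-dose sample is either the first (0.25 h) or the last (12 h).

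**Illustration 1: half-life 10 h, ka = 1 per h (ke = 0.0693).**
- C(0.25) ∝ 0.9828 − 0.7788 = 0.2040
- C(12) ∝ 0.4353 − 0.0000 = 0.4353
- Steady-state trough ∝ 0.4353 / (1 − 0.4353) = 0.7708
- Cmin by the SAP rule is the 0.25 h sample: 0.2040 / 0.4353 = 47% of the 12 h value, and 0.2040 / 0.7708 = 26% of the steady-state trough.

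**Illustration 2: half-life 4 h, absorption half-life 0.25 h.**
- C(0.25) ∝ 0.9576 − 0.5000 = 0.4576
- C(12) ∝ 0.1250
- Here the minimum is the 12 h sample.

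**Where the switch occurs (no lag).** The 0.25 h sample is the lower of the two only if the elimination half-life exceeds the value shown:

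| Absorption half-life (h) | 0.1 | 0.25 | 0.5 | 0.75 | 1.0 | 1.5 |
|---|---|---|---|---|---|---|
| Elimination half-life above (h) | 41.7 | 11.5 | 6.3 | 4.7 | 3.9 | 2.9 |

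With a lag of 0.25 h or more, the 0.25 h concentration is zero and is the minimum in every case.

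**How often.** Half-lives were drawn log-uniformly, with absorption half-life 0.1–1.5 h. The share of profiles with the minimum at 0.25 h, first with no lag and then with a lag uniform on 0–0.25 h, is:
- elimination half-life 2–24 h: about 42% and 65%
- 6–16 h: 59% and 83%
- 2–6 h: 13% and 37%

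**First dose against steady state.** Once absorption is complete, the Day 1 12 h value is a fraction 1 − exp(−12·ke) of the steady-state trough: 88% at a half-life of 4 h, 56% at 10 h, 50% at 12 h and 29% at 24 h. So the label matters even when the minimum does fall at 12 h.

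**Zeros.** With three subjects and one zero, the geometric mean is (0 × a × b)^(1/3) = 0. Computed through logarithms it is undefined, as is the geometric CV. The SAP gives no rule for this case.

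**The case against.** The strongest reply is that these are wording slips in a small descriptive substudy, and that most of what matters is already planned. Much of that stands.

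- **Frequency.** A reader might infer that Cmin will usually be the 15-minute sample. The documents do not support this. It depends on half-life, absorption rate and lag, none of which they give, and the share above runs from 13% to 83% across assumed ranges.
- **Exposure–response.** A reader might infer that the exposure–response analysis would use exposures that are too low. Protocol 11.3 bases that analysis on the sparse samples from all subjects, correlated with ALT change, not on the Day 1 profile.
- **Steady-state troughs.** SAP 6.10.3 already summarizes and plots the Week 8, 16 and 24 troughs by treatment group. The SAP itself never calls the Day 1 profile steady state; that phrase is in the protocol.
- **AUC.** First-dose AUC over 12 h would understate steady-state exposure. However, SAP 6.10.2 also plans AUCinf, CL/F and the extrapolated percentage. Under linear kinetics, first-dose AUCinf equals the steady-state AUC over an interval.
- **Dose choice.** No passage ties the recommended dose to Day 1 Cmin or AUC.
- **Moving the profile to Week 8.** A first-dose profile is a legitimate source of AUCinf, CL/F and half-life. Changing the day is a design trade-off that the defect does not require.

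None of this repairs the contradictory label, the Cmin definition or the missing rule for zeros.

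**Conclusion.** The point holds in limited form. On the documents alone, three things are wrong as written:

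- Protocol 11.3 calls a first-dose profile steady state, and Protocol 10.3.3.1 and SAP 6.10.1 count a sample taken before any drug towards steady-state assessment.
- The SAP's Cmin is not tied to the end of the interval, so it can be an absorption-phase value.
- Leading non-quantifiable values become zeros that the planned geometric summaries of Cmin cannot accommodate.

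The figures of 47% and 26% illustrate the size for one assumed pair of kinetic values. With faster absorption or a short half-life, the rule returns the 12 h sample. The effect is confined to descriptive parameters in about six subjects (three in each of two dose groups) and does not touch the primary analysis, safety or the stated exposure–response analysis. It is still worth correcting, because PK is a named secondary objective and the correction needs no new data.

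**What to change.** Wording changes only:

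1. In Protocol 11.3, delete the steady-state description of Day 1, and label the Day 1 parameters in both documents as first-dose.
2. In SAP 6.10.2, define Day 1 Cmin as the 12 h concentration, drawn before the second dose.
3. Report steady-state Cmin from the Week 8, 16 and 24 pre-dose samples, which are already drawn and summarized.
4. In SAP 6.10.1 and Protocol 10.3.3.1, remove the Day 1 pre-dose sample from those used for steady-state assessment. It can remain as a pre-treatment check.
5. In SAP 6.10.3, state how zeros enter geometric means and CVs: for example, report the number of non-quantifiable values and compute the geometric statistics on quantifiable values only. The rule should also cover the concentration summaries at each time point and the troughs, where non-quantifiable values are likewise set to zero.

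The cost is a short protocol clarification and an SAP revision before the PK parameters are computed. No samples, visits or subjects are added.

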11.4 Communication of Laboratory Results to Sites

All laboratory results will be communicated directly to sites by fax or other means. All laboratory results which equate to an NCI CTCAE grade 3 or above toxicity will be escalated for internal medical review by the contract research organization and/or medical monitor.

11.5 Study interventions

Peripheral blood collection: Blood will be collected venipuncture. Serum and plasma will be collected for assessing non-invasive biomarkers related to NAFLD / NASH as well as liver fibrosis (i.e. CK-18, adiponectin, leptin, TNF- α , TGF- β , hyaluronic acid, and MMP-2). MRI Procedures as detailed in Section 11.3.

Magnetic Resonance Imaging (MRI)

The purpose of the magnetic resonance imaging (MRI) exam is to quantify the hepatic proton density fat fraction non-invasively in participants who participate in the study. The fat fraction is the proportion of mobile protons in liver tissue attributable to fat and thus is a non-invasive MR-based assessment of liver triglyceride concentration. To quantify the fat fraction, the MRI exam will use a fast spoiled gradient recalled echo sequence that uses a low flip angle to reduce T1 bias, acquires multiple echoes after a single excitation to measure and correct for T2* decay, and uses spectral modeling to address fat-water and fat-fat signal interference effects. The proposed MRI technique measures hepatic fat fraction accurately in human subjects at 1.5T or 3T and across different vendors. The technique provides high within-examination and between-examination precision. Linearity is maintained across the entire relevant biological range from <1% to >40% hepatic fat fraction. The technique is robust to minor variations in acquisition parameters, including those that may be encountered during usage in a clinical trial. The echo sequence proposed for imaging-based hepatic fat fraction quantification can be implemented on any up-to-date clinical scanner and thus can be used at any clinical centers with access to such a scanner. Moreover, the technique is imaging based and covers the whole liver, thus providing information on both the quantity and distribution of hepatic fat fraction. MRI is currently the most accurate noninvasive technique to quantify hepatic fat fraction.

Percutaneous Liver Biopsy

The purpose of the liver biopsy within 12 months of screening is to ensure the presence of NASH and the absence of cirrhosis prior to randomization. The histologic features of liver injury (ie. necroinflammation, ballooned hepatocytes) and hepatic fibrosis is best assessed by liver biopsy as this remains the “gold-standard” for grading and staging NASH. The ideal target population “at risk” for disease progression, and thus, the appropriate cohort of subjects for investigational therapies are those patients with histologic evidence of NASH with hepatic fibrosis. Due to the early phase of investigation and the interdeterminate safety of JKB-121 in patients with cirrhosis, subjects with histologic features of cirrhosis (stage 4 fibrosis) and/or any history of hepatic decompensation attributable to cirrhosis will be excluded. The screening liver biopsy should be considered for patients with known history of NASH and for whom historical liver biopsy is in excess of 12 months. Given the dynamic changes in NASH which may occur due to life-style changes alone and the reassurance of targeting patient with histologic features of NASH, only patients with biopsy-proven NASH within 12 months of screening will be enrolled.

